#### 4.5 Methods of Minimizing Risk and Bias

Using a third party to hide the grouping will help reduce the errors caused by selection. The randomization will be proceed in operation, and the staff should set blinding to the subjects.

Operational errors could result in change in blood transfusion rate. To minimize this risk, we need to make sure that all operating rooms and recovery wards in each center use an unified blood transfusion plan. Each medical team within each center should have same start-up criterion for setting up blood transfusion. Before participating in the trial, each center should provide a blood transfusion plan to the leader center for record. Some centers would use a prespecified value of Hb to determine whether blood transfusion is needed and this value should be unified among each center's medical team. If any of the following symptoms presents, such as unconscious, dyspnoea, exhaustion, which could clearly indicate level of red cell, blood transfusion is needed. Maternal mobility and neonatal care after cesarean section are different from the postoperation rehabilitation activity of most bedridden patients. According to the practical issues, since the clinicians may have different point of view, it is allowed to have little variation between each center. It represents the difference in reality cross the clinic, so it will not increase the bias.

Postpartum ward medical staff should use an unified blood transfusion plan as far as possible, according to the postoperative Hb levels and maternal symptoms. Do not deliberately observe the grouping of subjects.

## 4.6 Preparation and Support for Medical Staff in the Trial

For obstetric, operating room nurses, obstetricians and anesthesiologists , who involve in the study, the application of intraoperative cell salvage during caesarean section surgery would be an extra workload. Especially in emergency caesarean section surgery, it would be more challenging to test how skilled clinicians are. Adequate training of all medical staff and the use of intraoperative cell salvage machine are very important to the success of trials. Intraoperative cell salvage needs to have been on-going at all participating centers, and many operating room staff should be highly-skilled in use of technology. Prior to the start of the trial, each center will need to provide a list of staff, who would involve in intraoperative cell salvage operations and have been assessed by the main investigators of each center. During the inspection, the CRA will assess the standardization of operations (SOP) of relevant staff.

## 4.7 Treatment Plan

According to local transfusion guidelines and medical staff's opinion (participant's Hb is lower than 70g/L before transfusion, or Hb is between 70~100g/L, depending on transfusion plan and medical staff.), women will be randomly allocated to either:

1. Caesarean section with IOCS(treatment group)
2. Caesarean section without IOCS. eg. donor blood transfusion(control group)

Theoretically, intraoperative blood transfusion need to be based on the following formula:

the volumn of blood transfusion needed(ml) \* Hb of transfusion samples =  $(Hb_2 - Hb_1) * \text{blood volumn}$ ,

where  $Hb_1$ :actual Hb;  $Hb_2$ : target Hb(100g/L)

blood volumn =  $100\text{ml/kg}^{10} * \text{weight}$

Either in treatment group or control group, the difference between the actual volumn of blood transfusion and the theoretical volumn should be controlled within  $\pm 15\%$  (in terms of mass of Hb).

### a. IOCS group

Eg.: Maternal actual Hb = 60g/L, weight = 60kg, Hb of blood sample = 200g/L

Column of blood transfusion needed = 1200ml, range of blood transfusions =  $1200 * (1 \pm 15\%)$ , 1020-1380ml; If there's insufficient column of self blood for five-minutes' infusion, then we use formula to calulate the column of blood transfusion needed. After five-minutes' infusion by self blood, if participant's Hb is still lower than 70g/L before transfusion, or Hb is between 70~100g/L, according to transfusion guidelines and medical staff's opinion, we continue to use formula to calulate the column of blood transfusion needed.

### b. Donor blood transfusion group

Eg.: Maternal actual Hb = 60g/L, weight = 60kg, assumed Hb of allogeneic red cell is 240g/L, per U red cell is around 200ml.

Volume of blood transfusion needed = 1000ml, range of blood transfusions = 1000\*(1±15%), 850-1150ml, around 4.25-5.75U; 4.5U red blood cell allogeneic blood can be requested from the blood bank. Following the concept of using of blood economically, we should take as less suitable blood as possible. If needed, we can communicate with the transfusion department. After five-minutes' infusion, we measure maternal's Hb again. If participant's Hb is still lower than 70g/L before transfusion, or Hb is between 70~100g/L, according to transfusion guidelines and medical staff's opinion, we continue to use formula to calculate the volume of blood transfusion needed.

When emergency life-threatening bleeding events happen in donor blood transfusion group (control group), based on the actual situation, clinical staff there can take the most reasonable step for mothers, including the intraoperative cell salvage. We expect the probability of this situation to be extremely low.

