## 8.2 Outcomes

### 8.2.1 Primary Outcomes

- Blood loss post operation

Hb and Hct in first and fifth day after surgery.

The direct measurement of is the accurate volume of blood loss in major haemorrhage is difficult. Alternatives such as haemoglobin (Hb) or hematocrit (Hct)

are more frequently used and blood loss can be calculated using these parametres. Since Hct or Hb will be recorded as per standard practice during and postoperative in the hospital.

In this proposed trial, we are planning that Hb and Hct in the first and fifth day after the surgery as the primary outcome to reflect the blood loss.

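### Only the donor-blood arm is told to economise within the ±15% haemoglobin band: a potential one-sided difference of about 4 g/L in the plan's own example

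*Combined protocol and SAP*

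**What the plan says.** Section 4.7 (Treatment Plan) sets a common rule. The volume to transfuse follows from one formula with a target Hb of 100 g/L, and the tolerance is common too: "Either in treatment group or control group, the difference between the actual volumn of blood transfusion and the theoretical volumn should be controlled within" ±15%, judged by haemoglobin mass.

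The two parts that follow apply this rule to a 60 kg woman with Hb 60 g/L.

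- Part a (IOCS): "Column of blood transfusion needed = 1200ml, range of blood transfusions" 1020 to 1380 ml. It does not say where in the band to aim.
- Part b (donor blood): the calculated volume is 1000 ml, with a range of "850-1150ml, around 4.25-5.75U". It then adds "4.5U red blood cell allogeneic blood can be requested from the blood bank" and "Following the concept of using of blood economically, we should take as less suitable blood as possible".

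Both parts share a repeat rule: the formula is applied again if Hb is still below 70 g/L, or if it is between 70 and 100 g/L and guidelines and staff opinion support it.

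Section 8.2.1 names "Hb and Hct in the first and fifth day after the surgery as the primary outcome to reflect the blood loss". Section 8.1.1 gives a blood-loss formula: blood volume times the fall in Hct from day 1 to day x, plus a transfused red cell volume Vt.

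**The concern.** A common target and band, expressed as haemoglobin mass, make sense only if the arms are meant to differ in the source of the red cells and not in the amount. An instruction to stay low in one arm works against that. The band limits the size of the deviation but does not balance it, because only one arm is pointed towards the lower edge.

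What is at stake is interpretation. If controls receive less haemoglobin, their postoperative Hb and Hct can be lower with no difference in bleeding. A difference in these levels between arms could then reflect less bleeding, more haemoglobin given, or both, and the planned analysis has nothing to separate them. The same applies to the Hb-dependent secondary outcomes in Section 8.2.2, such as the fall in haemoglobin and morbidity from postoperative anaemia.

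**Working it through.** **Inputs.** From Section 4.7: target Hb 100 g/L and blood volume 100 ml/kg. From parts a and b: weight 60 kg, actual Hb 60 g/L, salvaged blood 200 g/L. From part b: "assumed Hb of allogeneic red cell is 240g/L" and "per U red cell is around 200ml". From Section 8.1.1: pilot SD 709 ml.

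**Reproducing the plan's figures.**

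- Blood volume = 100 ml/kg × 60 kg = 6 L.
- Haemoglobin needed = (100 − 60) g/L × 6 L = 240 g.
- IOCS: 240 / 200 = 1.2 L = 1200 ml; ±15% gives 1020 to 1380 ml.
- Donor: 240 / 240 = 1.0 L = 1000 ml = 5 U; ±15% gives 850 to 1150 ml, or 4.25 to 5.75 U.

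All agree exactly with the document.

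**What the donor example orders.**

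- 4.5 U × 200 ml = 900 ml; 0.9 L × 240 g/L = 216 g.
- Shortfall = 240 − 216 = 24 g, which is 10% of the amount needed.
- Calculated Hb after transfusion = 60 + 216/6 = 96 g/L, or 4 g/L below target.
- At the band floor, 4.25 U: 0.85 L × 240 g/L = 204 g, giving 60 + 204/6 = 94 g/L, or 6 g/L below target.
- 4.5 U is the lowest half-unit step inside the band.

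The gap scales with the deficit. For a starting Hb of 50 to 90 g/L the deficit is 50 to 10 g/L, so a 10% shortfall is 5 to 1 g/L and a 15% shortfall is 7.5 to 1.5 g/L.

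**Does the repeat rule close the gap?** The remaining 24 g is 24/240 = 0.1 L, or 0.5 U. At 96 g/L the patient is in the 70 to 100 g/L zone, so this top-up is permitted but not required.

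**Effect on the outcome, by how the outcome is built.**

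1. *Raw day-1 or day-5 levels.* An uncorrected shortfall lowers control values and favours IOCS. Assuming 320 to 340 g Hb per litre of red cells (not given in the documents), 4 g/L corresponds to 4/340 to 4/320 = 0.0118 to 0.0125 in Hct. Multiplied by 6000 ml this is about 71 to 75 ml, roughly 0.10 to 0.11 of the SD of 709 ml.
2. *Section 8.1.1 formula, Hct term.* If the shortfall lowers Hct by the same d on both days, then (Hct1 − d) − (Hctx − d) = Hct1 − Hctx. The shift cancels.
3. *Section 8.1.1 formula, Vt term.* Its time window is not defined. If Vt includes intraoperative transfusion and is read as product volume, the donor example adds 900 ml instead of 1000 ml. That lowers computed control loss by 100 ml and favours control. Against the nominal 1200 ml in the IOCS example the difference is 300 ml, of which 200 ml comes from the different product concentrations and not from the economy wording.

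**The case against.** The strongest defence is that both arms work under the same target, band and repeat rule, and that donor patients have Hb measured again and can be topped up. The 4.5 U is worded as what may be requested from the blood bank, not as the total given. The IOCS arm can also fall short, since part a foresees too little salvaged blood. Sparing donor blood but not salvaged blood may be a fair picture of current practice, which is the stated comparator, and Section 1.1 calls blood scarce and expensive.

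Much of this stands. It does not remove the asymmetry. The top-up at 96 g/L is discretionary, and that discretion is exercised under an economy instruction in one arm only. Section 4.5 describes blinding of subjects; ward staff are merely asked not to look deliberately at the grouping. If the economy wording belongs to the comparator, Section 4.7 does not say so, and it sits beside a rule that points to equal haemoglobin mass.

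A reader might infer four stronger things that the documents do not support:

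- *That controls are systematically given less haemoglobin.* The shared repeat rule and possible IOCS shortfalls leave the net difference open.
- *That the primary outcome favours IOCS by design.* This holds only for raw levels; the formula-based loss may be unaffected or may favour control.
- *That the arms could be expected to differ by 12 g/L* (30% of a 40 g/L deficit). That needs IOCS patients at +15%, and nothing directs them there.
- *That control donor units and cost are inflated.* With a top-up, 4.5 + 0.5 = 5 U and the gap closes; without one, the gap stays but fewer units are used. Taken alone, the instruction lowers control donor units, which works against IOCS on that secondary outcome.

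**Conclusion.** The point holds as a potential one-sided co-intervention difference. In the plan's own example it is about 4 g/L before any discretionary top-up, and at most 6 g/L below target within the band. It would favour IOCS if raw day-1 and day-5 Hb or Hct are compared. For blood loss by the Section 8.1.1 formula the direction is undetermined.

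These sizes rest on the plan's own constants (100 ml/kg, 240 g/L, 200 ml per unit), on a starting Hb of 60 g/L, and on IOCS patients receiving the formula amount. The cancellation assumes an Hct shift that is equal on both days. The effect is modest, but it bears on a named primary outcome and is cheap to address.

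**What to change.** - **Reconcile Section 4.7 with its parts a and b**, so that the same rule for position within the ±15% band applies in both arms, or state the difference and justify it as part of the comparator. Which rule applies is a clinical decision for the sponsor.
- **Report actual divided by theoretical haemoglobin mass by arm**, and interpret Hb and Hct differences in light of it. Section 4.8 already schedules the recording of transfusions and of Hb. The sponsor should confirm that the Hb of the salvaged product is among the autologous transfusion data captured, since the table does not say.
- **State with that summary that donor Hb content is the assumed 240 g/L.**

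The cost is a wording change and one derived summary. The limitation is that the donor-arm figure rests on a constant: if the true content were 10% lower (216 g/L), 5 U would carry 1 L × 216 g/L = 216 g, the same shortfall as ordering 4.5 U.

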#### 4.8 Procedure Table

	Preoperative	Intraoperative	Postoperative	Hospital Discharge	Long-term Follow-up
Eligible criterion and Grouping					
Inclusion, exclusion criteria review	X				
Informed Consent Acquisition	X				
Record demographic information, contact info, diagnosis, type of surgery, cesarean section indication, birth history, preoperative blood loss, comorbidities (past history), blood group ABO, and other abnormalities		X			
Randomization (Dynamic Randomized)			X		
Blood Transfusion					
Intraoperative blood transfusion and other blood products		X	X		
Intraoperative autologous blood transfusion, and related data		X			
Maternal					
Intraoperative anesthesia operation time, special circumstances (such as hypotension), urine output		X			

Intraoperative and postoperative daily bleeding and transfusion, infusion volume (crystal, gel), blood-related drugs		X	X		
The highest body temperature, Hb / Hct / Plt, PT / APTT, ALT / AST / total G / D and renal function (creatinine and urea)	X	X	X		
Postoperative bleeding (drainage, bleeding, lochia, etc.)			X		
Specific causes of postoperative bleeding (uterine inertia, placental conditions, soft birth canal laceration situation)			X		
Test of blood component in recover blood and maternal blood fetal		X (Specimen only)	X (Specimen only)		
Transfusion reaction		X	X		
Other hospitalization					
Time to first mobilisation			X		
Duration of hospital stay				X	
Intraoperative and postoperative adverse events		X	X		
Reoperation caused by bleeding			X		
Inpatient mortality				X	
Overall medical expenses				X	
Tracking for hemolytic disease in future birth					X

## 4.9 Relevant Operating Plan

### 4.9.1 Assessment Method for Intraoperative and Postoperative haemorrhage in Obstetrics

- Assessment Method for Intraoperative blood loss in Cesarean Section
  - ❖ Weighing Method: blood loss (ml)  $\approx$  (weight of gauze with blood – weight of dry gauze) /1.05
  - ❖ Measuring Cup Method: used to measure amount of blood in a curved plate; blood loss ml=Volume of measuring cup (blood clots crush as much as possible).
  - Intraoperative blood loss = Recycling machine blood volume (recovery machine capacity - flushing, washing capacity) + Placental bleeding (using measuring cup to measure the amount of blood flow into the curved plate by

- squeezing the placenta) + blood volume of cleaning the vagina (bleeding with weighing method, blood clots with measuring cup method) + blood volume of gauze (bleeding with weighing method, blood clots with measuring cup method)
- Postoperative blood loss = blood volume of postpartum sterile mattress + blood volume of gauze (bleeding with weighing method, blood clots with measuring cup method) + volume of shed blood (using measuring cup)

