### 2.1 Study Objects

#### 2.1.1 Primary Objective

- Blood loss of the subjects in 5 days post operation

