## **8 Statistical Analysis**

### **8.1 Estimation of Sample Size**

#### **8.1.1 Sample Size Calculation**

In this study, we use data from control group (donor blood transfusion) to estimate the sample size, and then use 1: 1 ratio to calculate the sample size of IOCS sample.

The calculation is shown below:

A pilot study has commenced at the The 2nd Affiliated Hospital of Wenzhou Medical University, Zhejiang Province, China, involving women having Caesarean sections and the need for red cell transfusion. We collected a sample of 50 from the study and use the following formula to estimate the blood loss after the caesarean section:

Blood loss =  $BV * (Hct_{first\ day\ post\ operation} - Hct_{xth\ day\ post\ operation}) + Vt$   
 where BV is the blood volume, Vt is the volume of red cell (unit: ml), and Hct has a unit with decimal places.

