### 8.3.3 Hypothesis Test

Primary objective: The amount of blood lose post operation:

$$H_0: HR = \frac{\lambda_T}{\lambda_C} < 1, \quad H_1: HR = \frac{\lambda_T}{\lambda_C} \geq 1$$

$\alpha = 0.05$  (two-sided).

By Log-Rank test, if p-value is less or equal to 0.05, and the median amount of blood lose in treatment group is less than in control group, then the superiority of the treatment group relative to the control group holds.

Based on the Cox Proportional hazards model, hazard ratios and the 95% confidence interval (CI), if the lower bound of the CI is greater than 1, then the efficacy of the treatment group is better than that of the control group.

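### The variable that decides superiority is not fixed: raw Hb and Hct, an Hct-derived volume and a measured volume all stand in for postoperative blood loss

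*Combined protocol and SAP*

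**What the plan says.** Five places in the combined protocol and SAP bear on the primary variable.

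- **Section 2.1.1** gives the primary objective as "Blood loss of the subjects in 5 days post operation". It names no method of measurement.
- **Section 4.9.1**, part of the operating plan, gives an equation: "Postoperative blood loss = blood volume of postpartum sterile mattress + blood volume of gauze", to which it adds shed blood read in a measuring cup. It states no time window and does not call the result primary. The procedure table in 4.8 has postoperative bleeding recorded, so a measured volume will be collected.
- **Section 8.1.1** says it will "use the following formula to estimate the blood loss after the caesarean section": BV × (Hct day 1 − Hct day x) + Vt. The terms are explained only as "where BV is the blood volume, Vt is the volume of red cell (unit: ml), and Hct has a unit with decimal places". The day x, the rule for BV and the period covered by Vt are not given. The pilot statistics and the sample size rest on this formula.
- **Section 8.2.1** gives a reason for avoiding direct measurement ("The direct measurement of is the accurate volume of blood loss in major haemorrhage is difficult") and then says the investigators are "planning that Hb and Hct in the first and fifth day after the surgery as the primary outcome to reflect the blood loss". It neither cites the 8.1.1 formula nor says how Hb and Hct become one quantity. Sections 2.1.2 and 8.2.2 list Hct and Hb on the same two days as secondary.
- **Section 8.3.3** tests "Primary objective: The amount of blood lose post operation" and requires a lower median amount in the treatment group. It refers to none of the definitions above.

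**The concern.** A confirmatory superiority test needs one variable, identified before the data are seen. Here an analyst working from 8.3.3 has to choose among raw Hb, raw Hct, the 8.1.1 volume and the 4.9.1 volume, and nothing in that section settles the choice. The result could depend on it, because the quantities differ in scale, in the period they cover and in what moves them. The choice also decides whether the stated sample size has any basis, since the plan reports variability for only one of them. Listing Hb and Hct as both primary and secondary adds to the confusion: they cannot hold both roles in the same analysis.

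**Working it through.** **1. What the sample size refers to.** Inputs from section 8.1.1: multiplier 1.96, S = 709, δ = 200. The plan's formula gives n = (1.96 × 709 / 200)² = 48.28, rounded up to 49. The plan states 50, which is close enough to count as reproduced. Then 50 × 1.2 = 60 per arm and 120 in total, as stated. Both 709 and 200 are on the scale of the 8.1.1 formula. The documents give no SD for the 4.9.1 volume, and none for day-1 or day-5 Hb or Hct.

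**2. Scale.** BV × (difference in Hct) is a volume of red cells. The 4.9.1 sum is a volume of whole blood. For illustration, take BV = 100 ml/kg × 60 kg = 6000 ml (the rule and example weight in section 4.7) and Vt = 0:

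- An Hct fall of 0.05 gives 6000 × 0.05 = 300 ml of red cells. At an assumed Hct of 0.35 to 0.25 that is 300/0.35 = 857 ml to 300/0.25 = 1200 ml of whole blood.
- The plan's δ of 200 ml becomes 200/0.35 = 571 ml to 200/0.25 = 800 ml of whole blood.

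A given number of millilitres therefore means different things under the two definitions.

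**3. Window.** The Hct difference starts at the day-1 sample, so bleeding between the end of surgery and that sample is not in it. Section 2.1.1 speaks of 5 days after operation. Section 4.9.1 measures postpartum loss with no such gap, but sets no end. Section 8.1.1 leaves the end at day x, while 8.2.1 says day 5.

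**4. Dependence on dilution.** With BV = 6000 ml, an Hct change of 0.01, 0.02 or 0.03 from fluid shifts alone moves one woman's calculated loss by 60, 120 or 180 ml and leaves her measured loss unchanged. This shows that the measures can diverge in an individual. It does not show bias between arms: a shift common to both arms cancels, and the documents do not show a differential one.

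**5. Dependence on Vt.** Section 4.7 works an example for a 60 kg woman raised from Hb 60 to 100 g/L: 40 × 6 / 240 = 1.0 L of donor red cells, or 40 × 6 / 200 = 1.2 L of salvaged blood. If Vt were read as all product given, including during surgery, the example would add 1000 ml in one arm and 1200 ml in the other for the same mass of haemoglobin. That 200 ml gap comes only from product concentration. The plan does not say that Vt is meant this way, but it does not exclude it. If Vt is limited to red cells given between the two samples, intraoperative donor and salvaged cells drop out, because the day-1 Hct already reflects them.

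**The case against.** The strongest reply is that the plan has already chosen. Section 8.2.1 is the primary-outcome section; it sets direct measurement aside and names Hb and Hct on days 1 and 5. The sample size was built on an Hct formula. Section 4.9.1 is an operating procedure with no 5-day window and no claim to be primary. Most of this stands: the measured volume is not an equal candidate, and the Hct route is the better reading.

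It does not close the matter. Section 8.2.1 opens under blood loss and then names two laboratory values without joining them into one quantity. Section 8.3.3 compares a median amount of blood lost, which is a volume and not a raw Hb or Hct. The only equation labelled as postoperative blood loss is the one in 4.9.1. The Hct route itself leaves day x, BV and Vt open.

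A reader might infer more: that the trial has two primaries, that superiority may be claimed on whichever succeeds, and that the type I error is inflated by a calculable amount. The documents do not support this. No text lets a win on either version count. Section 8.3.3 also requires the difference to favour treatment, and any inflation figure would rest on a correlation that the documents do not give. A reader might also take the pilot's minimum and 25th percentile of 0 as proof that the formula fails to track real bleeding; the plan does not say how those zeros arose.

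**Conclusion.** The concern holds as an inconsistency in the definition of the tested variable. Three kinds of quantity (raw laboratory values, a calculated red-cell volume and a measured whole-blood volume) are attached to one endpoint name, and neither the objective nor the hypothesis test says which decides superiority. The difference in scale is roughly threefold to fourfold (1/0.35 = 2.9 to 1/0.25 = 4) at the assumed Hct range of 0.35 to 0.25, and the windows differ too. The millilitre illustrations assume a 60 kg woman and 100 ml/kg; the inconsistency does not depend on them. The SD of 709, the δ of 200 and the minimum of 50 can be cited only for the calculated version. It does not follow that the plan intends the measured volume as primary, or that the stated sample size is wrong for it: the information to judge the latter is not given.

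**What to change.** In 2.1.1, 8.2.1 and 8.3.3, name one and the same primary variable, the 8.1.1 calculated loss, and complete its definition:

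- set x to day 5;
- state the rule for BV;
- limit Vt to red cells given between the day-1 and day-5 samples, and say how it is expressed in ml;
- label the result as a red-cell volume lost from day 1 to day 5.

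Keep raw Hb and Hct as secondary only. Label the 4.9.1 measured volume as a prespecified supportive analysis that cannot carry the superiority claim. State that 709, 200 and 50 refer to the calculated version, and confirm that the pilot values used the same days and the same Vt period, since 8.1.1 does not say.

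The cost is wording: the plan already provides for collecting both kinds of measure. The sponsor gives up the choice between measures, and the primary result will not include bleeding before the day-1 sample; the measured volume can describe that period as supportive evidence.
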